6.3. Subjects

To be included in the investigation, the subjects must comply with the selection criteria described in section 0 and 6.3.2.

Subjects that has terminated the study will be informed to contact investigator in case of any questions during the study, and their general practitioner in case of any questions later than one week of investigation termination.

6.3.1. Inclusion criteria for subject selection

Subjects interested in participating the clinical investigation must comply with the following criteria:

Inclusion criteria	Justification for inclusion criteria
Has given written informed consent and signed letter of authority	To ensure voluntarily and that Helsinki Declaration is met. Letter of Authority is a demand from Danish Medicines and Health Authorities
Is at least 18 years of age and has full legal capacity	To meet Helsinki Declaration
Is a male	Males are considered 'worst case' since their urethra is longer
Willing to comply without using analgetica ² up to 24 hours prior to catheterisation visits	Pain relief could affect primary and explorative endpoints and general experience of catheterisation. The 24 hours are chosen based on use of most common analgesics (Ibuprofen, paracetamol and aperin) which have a half-life (T½) of two hours. Using safety equation of $T\frac{1}{2} \times 5$ hours gives ten hours, where 3% is left in the body. The 24 hours is given as safety margin and is more practical in the investigation
Has a negative urine multistix for erythrocytes (microscopic haematuria)	Haematuria is an explorative end point. If subjects have haematuria when entering the investigation, it could affect the evaluation of data. Haematuria could also be a sign of Urine Tract Infections (UTI) which is also an exclusion criterion
Definition of negative/positive results for Multistix erythrocytes: Negative Negative. Non-haemolysed 10 Ery/µL (+/-) Haemolysed 10 Ery/µL (+/-)	
Positive Non-haemolysed 80 Ery/µL (2+)	
Haemolysed 25 Ery/µL (1+) 80 Ery/µL (2+) 200 Ery/µL (3+)	
Has a negative urine multistix for leukocytes	To ensure that subject does not have UTI at inclusion
Definition of negative/positive results for Multistix Leukocytes: Negative Negative	
Positive 15 (1+)	

² Medicines for systemic use that are pain relieving without significantly affecting the consciousness

70 (2+)	
125 (3+)	
500 (4+)	
Has a negative urine multistix for nitrite	To ensure that subject does not have UTI at inclusion

6.3.2. Exclusion criteria for subject selection

Subjects complying with the following criteria must be excluded from participation in the clinical investigation:

Exclusion criteria	Justification for exclusion criteria
Has a previous history of genitourinary disease including congenital abnormalities and surgical procedures performed in the urinary tract	To ensure homogeneous group of urinary tracts where abnormalities, diseases or surgical procedures do not influence on the subjects perception of the catheters
Has symptoms of urinary tract infections (frequent urination, stinging and pain at urination)	To ensure that the subjects do not have UTI at inclusion. None of the symptoms may be present.
Are participating in any other clinical investigation related to urinary tract system during this investigation (inclusion to termination)	To eliminate uncertainty whether any Adverse Events (AE's) or Serious Adverse Events (SAE's) occurring during the study to relate to use of the herein tested products, and to eliminate unintentional affect from other devices/medicines on the study's data
Known hypersensitivity toward any of the test products	Asked by competent authorities

6.3.3. Recruitment and enrolment

Recruitment of potential subjects will begin once approvals have been obtained from the Danish Medicines Agency and the Ethics Committee. The recruitment process for this investigation is described in Table 3.

Table 3: Overview of the recruitment process

Recruitment method	www.forsøgsperson.dk	Advertisement
Potential subjects	Subjects will be recruited through www.forsøgsperson.dk where potential subjects can gather information on clinical investigations. The contact information for Clinical manager or a representative hereof will be available at the site.	Advertisement i.e. in local shops, sports facilities, local newspapers and social media. The advertisement will state the contact information for Clinical Manager or a representative hereof.
First contact	Interested potential subjects contact Clinical Manager at Coloplast A/S or a representative hereof.	
Second contact	The Clinical Manager, a representative hereof or the study personnel will contact interested potential subjects by phone and give a short introduction to the investigation.	
Subject Information Form		If a potential subject is still interested in participating, then written information about the investigation (subject information form) will be sent to the subject to ensure that potential subjects are given the opportunity to read about the investigation before a possible informational visit, and so that they can prepare any possible questions they may have. The subject information provides information to potential subjects about how to contact the investigator or a representative thereof, or a representative of the sponsor (name, telephone number and e-mail address), if they wish to learn more about the study.

	In addition, the potential subjects will receive an additional letter about subjects rights in Denmark: "Forsøgspersoners rettigheder i et sundhedsvidenskabeligt forskningsprojekt".
First visit	If a potential subject is interested in participating after reading the subject information form, a visit (visit 0) will be arranged in a room reserved to ensure privacy and quiet surroundings at the investigators clinic/department. When arranging the visit, it will be ensured, that the subject has received the Information Form prior to the visit.
Information visit	The subjects will receive both written and verbal information about the possibility of bringing a companion to the informational visit and to any possible subsequent visits. See section 13 for information to be given to the subjects, as well as the informed consent process.

6.3.4. Subject withdrawal criteria

The subject can withdraw from the investigation at any time for whatever reason without any consequences for their future treatment outside the clinical investigation. Investigator may withdraw a subject from the investigation at any time if they judge it to be the subject's interest.

The investigator must withdraw a subject from the investigation due to:

- Non compliance with the CIP impacting the scientific integrity of the investigation.
- If subject's safety and wellbeing is compromised by further participation.

A subject who is withdrawn from the investigation, for any reason, will be encouraged to contact the investigator if problems arise that the subject believes are related to the clinical investigation. Subjects who have not experienced any adverse events will not be followed up. For subjects who experience adverse events, see section 14.

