4.2. Anticipated risks, side effects and disadvantages

Risks associated with the investigation may be discomfort or stinging in the urethra during the catheterisation. Furthermore, there may be a risk of micro trauma and haematuria after catheterisation, which heals within 1-3 days. The test catheter is not expected to produce more stinging or discomfort compared to any other standard catheter on the market.

Possible interactions with concomitant medical treatments

There is no known interaction between the use of catheters and concomitant medication. However, the use of analgesics must be avoided up to 24 hours prior to catheterisation visits during this investigation, since pain relief could affect primary an explorative endpoints and general experience of catheterisation.

Steps that will be taken to control or mitigate the risks

All subjects are encouraged to contact the investigator in case of problems or unwanted side effects. During the investigation, all subjects will be enquired about their health and eventual problems (including issues mentioned here) by the investigator or representative at every visit. In addition, trained health professionals will perform the catheterisations.

Risk-to-benefit rationale

The risk and disadvantage of participating in the investigation are estimated to be low. The healthy volunteers will not have any benefits from this investigation, but catheter users may in the future benefit from a new and improved catheter and methods for faster voiding.

5. Objectives and hypotheses of the clinical investigation

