14.1. Adverse events

14.1.1. Adverse event

An adverse event is any untoward medical occurrence, unintended disease or injury, or untoward clinical signs (including abnormal laboratory findings) in subjects, users or other parties, whether related to the medical device(s), or the procedures involved. This could include events such as headache or dizziness.

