14.4. Medical care of subjects

Principal investigator shall ensure that adequate medical care is provided to a subject experiencing an adverse event during and after participation in the clinical investigation. All serious adverse events will be followed until a resolution is addressed.

Subjects are informed to contact investigator if any adverse event should occur during the investigation. Furthermore, investigator will inform the subjects to contact him should serious adverse events occur within one week of the subject is terminated from the study. Subjects are informed to contact their general physician in case of any adverse event(s) happening later than one week of investigation termination.

The status of all ongoing adverse events is documented during site close-out.

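### Section 6.3.4 schedules no active enquiry about delayed non-serious adverse events after a withdrawn subject's last catheterisation (minor)

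*Combined protocol and SAP*

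**What the plan says.** Section 6.3.4 gives the rule for withdrawals: "Subjects who have not experienced any adverse events will not be followed up". A withdrawn subject instead "will be encouraged to contact the investigator if problems arise that the subject believes are related to the clinical investigation". The next sentence sends the other group elsewhere: "For subjects who experience adverse events, see section 14".

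Other sections bear on the same subject:

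- Section 14.4: "Subjects are informed to contact investigator if any adverse event should occur during the investigation". After exit, the "investigator will inform the subjects to contact him should serious adverse events occur within one week of the subject is terminated". Events more than a week after termination go to the general physician.
- Section 4.2 invites all subjects to get in touch about problems or side effects. It also has staff ask about health at each visit.
- Section 6.4.1 requires UTI-symptom questions and a dipstick for erythrocytes, leukocytes and nitrite before every catheterisation. Section 6.1 sets at least five days between catheterisations.
- Section 6.1 and the flow chart in 6.4.4 list a termination visit, and the flow chart collects adverse events there. Section 6.4.1 has the termination page filled in at the end of Test Visit 6.
- Section 7.1 places every consenting subject who received any product in the safety population. Adverse events are a secondary endpoint (6.1.1) and will be summarised or listed.

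**The concern.** The plan collects delayed events after each product mainly through the next visit. A subject who leaves after Test Visit 1 or 2 with nothing yet recorded has no next visit, and 6.3.4 puts no other active enquiry in its place. He is left to report on his own initiative, and 6.3.4 frames that around what he himself attributes to the study.

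That is narrower than the endpoint it feeds. Section 14.1.1 defines an adverse event "whether related to the medical device(s), or the procedures involved" without making relatedness a condition. Relatedness enters only in 14.1.2, where it separates adverse device effects from other events.

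Because the subject stays in the safety denominator, silence is read as no event. Section 3 says the prototypes have not been tried in the human urethra before, so complete collection of delayed events is worth a small effort.

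**Working it through.** The plan states no figure on this point: no formal sample size calculation (7.2) and no drop-out expectation (7.4 reads NA). The check is therefore mainly a comparison of sections, with a short calculation for scale.

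**Step 1. Which routes could capture a delayed non-serious event after withdrawal?**

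| Route | Who starts it | Relatedness condition | Reaches this event? |
|---|---|---|---|
| Health questions at visits (4.2) | Staff | None | No, he attends no further visit |
| Symptom check and dipstick before the next catheterisation (6.4.1) | Staff | None | No, same reason |
| Contact after withdrawal (6.3.4) | Subject | His own belief | Only if he calls |
| General invitation (4.2) | Subject | None | Only if he calls |
| Any event during the investigation (14.4) | Subject | None | Only if he calls, and only if the phrase extends beyond his own exit |
| Serious events within one week (14.4) | Subject | None | No, serious events only |
| Termination visit (6.1, 6.4.4) | Staff | None | Unclear, no section says a withdrawn subject attends |

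Every route that clearly applies depends on the subject. The one staff-initiated route that might apply, the termination visit, sits uneasily with the no-follow-up sentence.

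**Step 2. Which events are exposed?** Section 4.2 says "there may be a risk of micro trauma and haematuria after catheterisation, which heals within 1-3 days". Visible blood is assessed during catheterisation, and the dipstick is repeated 1-2 hours later at the same visit. Stinging is listed in Table 5 as occurring during catheterisation. These are recorded before the subject leaves. What remains is delayed: mainly UTI, or dysuria or bleeding that starts later.

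**Step 3. How large could the loss be?** Inputs:

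- Withdrawals w = 1, 2 or 3 of ten subjects. This is an assumption, because the plan forecasts none.
- Each has one last catheterisation without a later enquiry.
- p is the upper limit of a Table 5 band, taken as the chance of a late event after that catheterisation (also an assumption): 1% for UTI, and 10% as a generous ceiling for any other late event, for which the plan gives no rate.

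Chance of at least one late event = 1 − (1 − p)^w.

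| w | p = 1% | p = 10% | Share of Part A catheterisations |
|---|---|---|---|
| 1 | 1.0% | 10% | 1/30 = 3.3% |
| 2 | 1 − 0.99² = 2.0% | 1 − 0.90² = 19% | 2/30 = 6.7% |
| 3 | 1 − 0.99³ = 3.0% | 1 − 0.90³ = 27% | 3/30 = 10% |

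The 30 is ten subjects times three products (Table 2). For a single product with ten Part A exposures, one withdrawal leaves 1/10 = 10% without later enquiry. That is a share of exposures, not of events. The chances above are for an event occurring. The chance of missing one is lower, since some subjects will call.

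**The case against.** The strongest reply is that the plan leaves several doors open and the practical effect is slight. Much of this stands, and it rules out three stronger readings.

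- **That a later event counts only if the subject calls and blames the study.** The documents do not support this. The request for serious events within one week (14.4) and the general invitation (4.2) carry no relatedness filter. They do still depend on the subject.
- **That the product which prompted withdrawal will look safer.** The no-follow-up sentence covers only subjects without an adverse event. A subject who leaves because of a recorded event is referred to section 14. Stinging and pain during catheterisation is itself a listed effect, rated 51-90%, so many unpleasant catheterisations would take the subject out of the rule. The direction of any bias between products is not shown.
- **That haematuria in general is lost.** Most of it would be seen at the visit. Only later bleeding is exposed.

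It is also fair to say that adverse events are only summarised or listed, with ten subjects and no success criteria. The gap may not be peculiar to withdrawals either. If the termination page is completed at Test Visit 6, completers may also have no later enquiry after their last catheterisation. That is a reason to settle the termination visit for everyone.

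None of this supplies a scheduled enquiry for the withdrawn subject.

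**Conclusion.** The point holds as a minor one. No section clearly schedules active enquiry about delayed non-serious events after a withdrawn subject's last catheterisation, while continuing subjects are asked and tested at least five days later. Since withdrawn subjects remain in the safety population, delayed events may be under-counted.

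The size is small: at most about 1% per withdrawal for UTI, if the Table 5 band is taken to apply to each catheterisation. The total depends on a number of withdrawals that the plan does not give. Conclusions on effects observed during the visits are untouched.

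**What to change.** Replace the no-follow-up sentence in 6.3.4 with wording such as: *Every withdrawn subject who has been catheterised and agrees to be contacted is asked once by phone, no earlier than five days after his last catheterisation, about all adverse events, whether or not serious and whether or not related. The result, or his refusal, is entered on the termination page.* Five days matches the minimum interval before a continuing subject is next asked. The call restores the questions but not the dipstick.

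Also reconcile 6.1, 6.3.4, 6.4.1, the flow chart in 6.4.4 and 14.4, so that they state whether the termination visit's adverse event enquiry applies to withdrawn subjects and when it takes place for completers.

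The cost is a short text change and one brief call per withdrawn subject by existing staff. A subject may decline the call. No treatment or care rule changes.

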6.3.5. Point of enrolment

A subject is considered enrolled in the investigation when the written informed consent is obtained. The expected duration for each subject is described in section 6.1.

6.3.6. Total expected duration of the clinical investigation

The dates below are approximate and no subjects will be enrolled before all required approvals have been obtained. Changes greater than \pm 3 months will be notified to EC and regulatory authorities.

- Submission to Ethics Committee and Competent Authorities (Mid March 2018)
- First subject enrolled (AUG/2018).
- Last subject enrolled (NOV/2018).
- Last subject completed (JAN/2019).
- Data Presentation (FEB/2019)
- Final report (DEC/2019).

6.3.7. Total number of subjects

As this is an exploratory investigation no formal sample size calculation has been performed. It is assumed that ten subjects will be adequate for obtaining indications on performance and acceptance.

6.4. Procedures

6.4.1. Clinical investigation-related procedures

Before initiation of the clinical investigation, sponsor must be provided with key personnel's signed and dated curriculum vitae (not more than two years old) to verify their qualifications. Key site personnel are those, who treat or evaluate subject data in the clinical investigation. Also, the sponsor will ensure that all site personnel are trained in the investigation procedures, how to complete the CRFs, procedure for reporting an adverse event or serious adverse event (how, when, to whom), and who to contact in case of emergency related to the investigational device.

The investigation consists of an inclusion visit and five test visits. For an overview see flow-chart in section 6.4.4.

Inclusion visit (V0) – approx. one hour

Information:

If a potential subject is interested in participating after the short oral introduction by phone and reading the subjects information form, an information visit will be arranged in a room reserved to ensure privacy and quiet surroundings at the site. When arranging the visit, it will be ensured, that the subject has received the Subject Information Form prior to the visit. The subjects will receive both written and verbal information about the possibility of bringing a companion to the informational visit and to any possible subsequent visits. During the information visit the Investigator or delegated personnel will provide oral information about the investigation based on the Subject Information Form. The subjects have the right to wait 24h before deciding on participation. The information visit and the Visit 0 can be the same day.

Informed consent:

If/when the subject decides to participate he will be asked to sign the Informed Consent Signature Form and other relevant forms (see section 13). If a subject so desires, and it is certain that it is understood what the investigation entails and the relevant forms have been signed, it is then ensured that in- and exclusion criteria are met, including urine analysis (leukocytes, nitrite and erythrocytes). Enrolled subjects are allocated a subject number, randomisation is performed and hereafter demographics, baseline data and concomitant medications is recorded by Investigator or delegated personnel.

Visit 0 and Test Visit 1 can be combined.

Test Visit (V1-V3) – approximately two hours

Subject is asked about symptoms for urinary tract infections (frequent urination, stinging or pain at urination) and use of analgetica up to 24 hours prior to the visit. In addition, a urine sample is made and microscopic haematuria, nitrite and leukocytes is measured before catheterisation to further ensure no symptoms of urinary tract infection or damage to the urinary tract system. If negative for these symptoms, use of analgetica and microscopic haematuria/nitrite/leukocytes, the subject will be catheterised with the randomised product and urine flow rate is measured. Hereafter the bladder is scanned for post void residual urine, by using a hand held bladderscanner, [REDACTED]. The subject is offered something to drink and after 1-2 hours a urine sample is made and microscopic haematuria measured. Subject and nurse register relevant answers in CRF, including possible adverse events. In addition, subject register the end points regarding discomfort (VAS-scale) and the nurse register the assessments in the CRF. Next visit is scheduled.

If subjects have agreed to participate in interviews, Test Visit 3 will be prolonged to include interview.

Test Visit (V5-V6) – approximately two hours

Subject is asked about symptoms for urinary tract infections (frequent urination, stinging or pain at urination) and use of analgetica up to 24 hours prior to the visit. In addition, a urine sample is made and microscopic haematuria, nitrite and leukocytes is measured before catheterisation to further ensure no symptoms of urinary

tract infection or damage to the urinary tract system. If negative for these symptoms, use of analgetica and microscopic haematuria/leukocytes/nitrite, the subject will be catheterised with the randomised product [REDACTED] [REDACTED] and urine flow rate is measured. Hereafter the bladder is scanned for post void residual urine, by using a hand held bladderscanner, [REDACTED]. The subject is offered something to drink and after 1-2 hours a urine sample is made and microscopic haematuria measured. Subject and nurse register relevant answers in CRF, including possible adverse events. In addition, subject register the end points regarding discomfort (VAS-scale) and the nurse register the assessments in the CRF. Next visit is scheduled.

If subjects have agreed to participate in interviews, Test Visit 6 will be prolonged to include interview. At the end of Test Visit 6 the termination page in CRF is completed by nurse.

Interview – plus one hour

Subjects will be asked if they would like to participate in interviews following Test Visit 3 and 6. A Coloplast representative will interview the subjects asking questions related to their experience with the catheter. The subjects will be asked to sign a specific consent form to participate in interview. In addition, subjects will be asked for consent to tape recording and filming during the interviews, but can participate in interviews without this. The investigator and/or study personnel will be interviewed by a Coloplast representative asking questions related to their experience with the catheters.

Urinary tract infection suspicion

If the subject shows symptoms of urinary tract infections he will be referred to his own physician for further examination. When the subject has been examined and treated for eventual urinary tract infections, and shows no symptoms for urinary tract infections, his visits can be rescheduled if possible before LPO. If not possible to complete all visits before LPO, the subjects should complete all possible visits.

Use of analgesics

If the subject used analgesics within 24 hours prior to a visit, this will be documented in the Concomitant Medication Form and the visit will be rescheduled.

